STU#:

NCT05082142

Tranexamic Acid to Improve Same-day Discharge Rates After Holmium Laser Enucleation of the Prostate (HoLEP)

10/29/2021

Protocol

STU#:

PROTOCOL TITLE: Tranexamic acid to improve same-day discharge rates after Holmium Laser Enucleation of the Prostate (HoLEP)

PRINCIPAL INVESTIGATOR:

[name]
Department of Urology
[contact]

VERSION DATE:

10.29.2021

STUDY SUMMARY:

Investigational Agent(s) (Drugs or Devices)	Tranexamic acid
IND / IDE / HDE #	
Indicate Special Population(s)	 Children  Children who are wards of the state  Adults Unable to Consent  Cognitively Impaired Adults  Neonates of Uncertain Viability  Pregnant Women  Prisoners (or other detained/paroled individuals)  Students/Employees
Sample Size	110
Funding Source	Department of Urology
Indicate the type of consent to be obtained	 Written  Verbal/Waiver of Documentation of Informed Consent  Waiver of HIPAA Authorization  Waiver/Alteration of Consent Process
Site	 Lead Site (For A Multiple Site Research Study)  Data Coordinating Center (DCC)
Research Related Radiation Exposure	 Yes  No
DSMB / DMC / IDMC	 Yes  No

OBJECTIVES:

This study is designed to assess if there is a significant difference in same day discharge rates after Holmium Laser Enucleation of the Prostate (HoLEP). We attempt to perform HoLEP as a same-day discharge (SDD) procedure, but at NM, our SDD rate is currently approximately 60%. The limiting factor in SDD is hematuria. Tranexamic acid (TXA) is a clot promoting drug that is commonly used by orthopedic, cardiac and obstetric surgeons to prevent bleeding. Our

STU#:

primary outcome will be to assess if there is a difference in SDD rates in those who receive TXA vs. those who do not.

Secondary outcomes will assess bleeding complications (defined as unplanned ED visit/clinicvisit/procedure/admission related to bleeding, clot retention, clot evacuation, need for perioperative transfusion) between patients who receive TXA vs. those do not. We will also assess differences in perioperative complications associated with TXA including but not limited to: deep venous thrombosis, pulmonary embolism, cerebrovascular events, between the groups. We will also assess for the duration of postoperative hematuria between groups. Additionally, we will assess for differences in operative times between the groups.

We anticipate that there may be up to a 25% increase in SDD rates in those who receive TXA vs. those who do not.

BACKGROUND:

Holmium Laser Enucleation of the Prostate (HoLEP) is a size-independent treatment option for benign prostate hypertrophy (BPH) as recommended by the American Urological Association (AUA) Guidelines.¹ Furthermore, HoLEP is one of the few surgical options that is recommended by the AUA for patients on active anticoagulation given its superior hemostatic properties.¹ [name] research team has previously shown that same-day catheter removal and same-day discharge (SDD) was successful in approximately 87% of patients.² This study was performed in a limited cohort of 207 patients. [name] was recently recruited to Northwestern Medicine to introduce HoLEP to Chicago. Our current SDD rate is approximately 60%. Factors limiting discharge are primarily related to the degree of hematuria and patient anxiety.

Tranexamic Acid (TXA) is an indirect fibrinolytic inhibitor and was discovered in the early 1960s.³ Although it was initially only used in women with heavy menstrual blood loss and those with hereditary bleeding disorders, it is now widely used in trauma situations and orthopedic, cardiac, otolaryngologic, and obstetric surgeries as it is cheap, safe, and effective.³ Oral, IV, topical and combined methods of TXA administration also reduced blood loss and risk of transfusion compared to placebo for patients undergoing total hip arthroplasty.⁴ TXA is safe, but high doses of TXA (80-100 mg/kg) or TXA use in those with poor renal function have been associated with an increased risk of seizures.⁵ While there is no clear evidence of increased risk of thromboembolic events⁶, it should be used cautiously in those with a history of embolic events, those on hormonal contraceptives.⁷

Use of TXA in Urologic literature has been limited. One prospective, randomized controlled trial studied the use of TXA in 40 men undergoing transurethral resection of the prostate (TURP).⁸ The authors found that TXA resulted in significantly less postoperative serum hemoglobin drop, less hemoglobin loss per gram of resected tissue, shorter OR time, and more resected tissue.⁸ In another prospective, randomized controlled trial, the authors randomized 136 men undergoing TURP to receiving TXA or not.⁹ The authors found TXA resulted in reduced operative blood loss, the amount of blood loss per gram of resected tissue, and shorter OR time. Interestingly, TXA did not decrease length of stay or catheter duration.⁹ In one systematic review analyzing the effects of TXA after transurethral resection of the prostate, the authors included nine studies in their meta-analysis and found that TXA reduced intraoperative estimated blood loss as well as the transfusion rate.¹⁰ The use of TXA in percutaneous nephrolithotomy (PCNL) has also been studied. A randomized, double-blinded, placebo-controlled trial enrolled 192 patients with Guy's stone scores III-IV. Patients were given 1g of IV TXA vs. placebo at time of anesthetic induction. The authors found that TXA administration during PCNL resulted in reduced blood transfusion rate, and higher stone free rates in the immediate postoperative period and at 3 months.¹¹

Although HoLEP is one of the few surgical options recommended by the AUA for patients at high risk of bleeding due to its excellent hemostatic properties, for patients undergoing same-day discharge, hematuria is often the rate limiting factor. Currently, no studies have examined the use of TXA during HoLEP. Therefore, we would like to study if the use of TXA during HoLEP will increase our SDD rates.

STUDY ENDPOINTS:

Primary:

- 1) Difference in same-day discharge and same-day catheter removal rates

Secondary:

- 2) Difference in medical events: defined as unplanned ED visit/clinic visit/procedure/admission related to bleeding, clot retention, clot evacuation, need for perioperative transfusion
- 3) Duration of postoperative hematuria
- 4) Difference in operative, enucleation and morcellation times
- 5) Adverse events related to TXA (thrombotic events (DVT, PE, stroke), seizures,

PROCEDURES INVOLVED:

Visit 1 – Screening (Day -45 – Day 0)

- i. Patients will complete:
 - 1) Patient Informed Consent Form,
 - 2) HIPAA form,
- ii. Investigative site will complete: patient demographics, medical history, Inclusion/Exclusion Criteria
- iii. Randomization and instructions to patients on whether or not to receive TXA

Visit 2 – HoLEP (Day 0)

- iv. Inclusion/Exclusion Criteria to reconfirm eligibility (only if Screening and HoLEP are not on the same day)
- v. Adverse Events secondary to TXA

Catheter Removal (Day 0 or 1)

Assessment of same day discharge and catheter removal rates

Week 1 through resolution of hematuria

The patient will receive a weekly computer generated text from Twilio (secure software integrated to REDCap) asking them to report their hematuria and dysuria after the procedure. It will also ask if they have had any unplanned visits or interventions. This will continue until 12 week post HoLEP survey

Visit 3 – One month follow-up (Day 30)

If patients have already reported resolution of hematuria, they will receive an additional questionnaire 30 days postoperatively to assess for bleeding complications and symptoms.

Visit 4 – Follow-up (12 weeks Post HoLEP)

- vi. Patient will be assessed for BPH symptom related questionnaires in addition to urinary parameters. Will also confirm if there were or were not bleeding or other complications in first 90 days postoperatively.

Early Withdrawal Patients: The investigator will make reasonable attempts to ensure all enrolled patients complete the study.

****If the patient is unable to complete the questionnaires by text, they will be contacted by phone call for questionnaire completion.**

STU#:

The HoLEP procedure is performed in a similar fashion by all surgeons with similar postoperative care plans. Duration of postoperative catheterization is determined by the treating surgeon, with respect to time of surgical case completion, need for inpatient observation, and patient preference. The portions of the case will not be altered regardless of patient being on anticoagulation or not, however the surgeon will not be blinded to the patient's status of anticoagulation therapy, as this knowledge would be paramount in postoperative management if there were complications.

DATA AND SPECIMEN BANKING

Data will be collected and stored electronically in REDCap. Quality assurance steps will include testing of database including any potential data calculated by command functions within REDCap (ex: age of patient at time of surgery calculated by using patient's date of birth and date of surgery) by study team prior to moving to production mode. The following quality control methods will be used: 1) single entry of data with random checks of accuracy, and 2) extraction and cleaning of data on a monthly basis that will be used for analysis every 3 months until completion of enrollment.

Data will be accessible to only authorized members of the study team. Any presentations on the study or published findings will use only de-identified data.

Data will be stored for 7 years after the end of the study. After this period, electronic data will be deleted.

SHARING RESULTS WITH PARTICIPANTS

Study results will not be shared with participants.

INCLUSION AND EXCLUSION CRITERIA

Inclusion Criteria

- Males 18 -89 undergoing HoLEP
- Willing to sign the Informed Consent Form
- Able to read, understand, and complete patient questionnaires, pain texts, and medication diary.

Exclusion Criteria

- Allergy or hypersensitivity to TXA, history of acute venous or arterial thrombosis, intrinsic risk for thrombosis or thromboembolism, history of thromboembolic disease, hereditary thrombophilia, use of hormonal agents
- Patients having a concurrent ureteroscopy +/- laser lithotripsy, percutaneous nephrolithotomy, or non-urologic surgery at the time of their HoLEP
- Anticipated need for perineal urethrostomy at the time of HoLEP
- Patient not undergoing catheter removal and voiding trial at Northwestern Memorial Hospital

PARTICIPANT POPULATION(S)

Accrual Number:	Category/Group: (Adults/Children Special/Vulnerable Populations)	Consented: Maximum Number to be Consented or Reviewed/Collected/Screened	Enrolled: Number to Complete the Study or Needed
-----------------	---	---	--

STU#:

			to Address the Research Question
Local	0	110	110
Study-wide	0	110	
Total:	0	110	110

RECRUITMENT METHODS

Enrollment into the study will be performed by a qualified research coordinator.

After the patient completes their pre-surgical enrollment paperwork in the clinic, they will then be met in a private room away from the treating physicians by a qualified research coordinator who will discuss their potential enrollment and complete any research paperwork. Some patients may be approached via telephone with virtual consent.

Therefore, the initiation of enrollment will begin at the time of the office consultation visit. The patient will remain enrolled until she/he has completed the post-procedure follow up clinic/virtual visit at week 12. Data will not be collected beyond when the patient is seen at the postoperative clinic visit. If the patient is unable to have a physical or virtual visit, a text follow-up will be performed.

After consenting, patients will be randomized to one of two groups.

Group 1 (control): Receive intraoperative 1g TXA

Group 2 (experimental): No TXA

Randomization to **Group 1** or **Group 2** will be allocated through REDCap.¹² The stratified randomization list will be created and provided by the study statistician before the start of patient recruitment.

COMPENSATION FOR PARTICIPATION IN RESEARCH ACTIVITIES

Patients will not be compensated for participating in this research.

WITHDRAWAL OF PARTICIPANTS

If a subject wishes to withdraw from the study, he/she may do so by verbal request to the research team. A subject may be withdrawn from the study by a physician-investigator if determined to be in the subject's best interest for medical reasons.

RISKS TO PARTICIPANTS

The risks in this study are no greater than the risks incurred during a HoLEP. AUA and EAU guidelines support HoLEP as a size independent treatment option for BPH.

Common side effects of TXA are nausea, vomiting, diarrhea, and muscle pain.

POTENTIAL BENEFITS TO PARTICIPANTS

Patients in the TXA arm may have higher rates of success with same day discharge and same day catheter removal.

DATA MANAGEMENT AND CONFIDENTIALITY

Data will be collected and stored electronically in REDCap. Quality assurance steps will include testing of database including any potential data calculated by command functions within REDCap (ex: age of patient at time of surgery calculated by using patient's date of birth and date of surgery) by study team prior to moving to production mode. The following quality control methods will be used: 1) single entry of data with random checks of accuracy, and 2) extraction and cleaning of data on a monthly basis that will be used for analysis every 3 months until completion of enrollment.

PROVISIONS TO PROTECT THE PRIVACY INTERESTS OF PARTICIPANTS

Data will be collected and stored electronically in REDCap and will only be accessible to members of the study team.

Data resulting from this study will not be linked to subjects. Subjects will not be referred to by name of initial in any publications.

CONSENT PROCESS

Enrollment into the study will be performed by a qualified research coordinator.

After the patient completes their pre-surgical enrollment paperwork in the clinic, they will then be met in a private room away from the treating physicians by a qualified research coordinator who will discuss their potential enrollment and complete any research paperwork. Some patients may be approached via telephone with virtual consent.

PROTECTED HEALTH INFORMATION (PHI AND HIPAA)

HIPAA authorization will be obtained as part of the consent. PHI from medical records and information collected from research and tumor samples will be protected by using coded subject numbers. The coded identifiers will be stored on a password protected spreadsheet stored on the FSM Urology server.

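### Patients are randomised and told their arm at screening, up to 45 days before an intraoperative drug, although patient anxiety and preference feed into the primary endpoint

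*Protocol*

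**What the plan says.** **Timing of allocation and disclosure.** In the Protocol, Procedures Involved, Visit 1 is labelled "Screening (Day -45 – Day 0". Item ii of that visit covers the eligibility criteria, and item iii is "Randomization and instructions to patients on whether or not to receive TXA". Recruitment Methods agrees: "After consenting, patients will be randomized to one of two groups". It also says that enrolment starts at the office consultation and that some patients are approached by telephone.

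**Timing of treatment and recheck.** Recruitment Methods has TXA given intraoperatively and compared with no TXA; no placebo is described. Visit 2, item iv, provides for "Inclusion/Exclusion Criteria to reconfirm eligibility (only if Screening and HoLEP are not on the same day".

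**What drives the endpoint.** Study Endpoints makes same-day discharge and same-day catheter removal primary.
- Objectives: "The limiting factor in SDD is hematuria".
- Background, last paragraph: "hematuria is often the rate limiting factor".
- Background, first paragraph: "Factors limiting discharge are primarily related to the degree of hematuria and patient anxiety".
- Procedures Involved, paragraph on the HoLEP procedure: "Duration of postoperative catheterization is determined by the treating surgeon, with respect to time of surgical case completion, need for inpatient observation, and patient preference".

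**Expected benefit.** Potential Benefits to Participants says that the TXA arm may do better on these same two outcomes.

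**The concern.** Two separate risks follow, and neither is needed to run the trial.

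1. **Disclosure.** A patient who knows whether he is to receive the drug may be more or less anxious about going home, or about having the catheter out. The protocol names anxiety as an input to discharge and preference as an input to catheter duration. Knowledge of the arm can therefore reach both parts of the primary endpoint without any effect of TXA on bleeding.
2. **Allocation before the recheck.** Between Visit 1 and surgery a patient may withdraw, a physician-investigator may withdraw him for medical reasons, or the Day 0 recheck may exclude him. All of these can happen with the arm known, so losses may differ between arms.

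If either risk is realised, part of an observed difference in same-day discharge or catheter removal would not be attributable to the drug. The point concerns events after allocation only. The randomisation list is prepared before recruitment and held in REDCap, and no failure of concealment at enrolment is alleged.

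**Working it through.** **Step 1: order of events, when Visit 1 precedes the day of surgery**

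| Event | When | Source in the Protocol |
|---|---|---|
| First eligibility check | Day -45 to Day 0 | Visit 1, item ii |
| Randomisation; patient told his arm | Day -45 to Day 0 | Visit 1, item iii |
| Eligibility recheck | Day 0 | Visit 2, item iv |
| TXA or no TXA | Day 0, in theatre | Recruitment Methods |
| Discharge and catheter removal assessed | Day 0 or 1 | Procedures Involved, Catheter Removal |

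Nothing the patient must do between the second and fourth rows depends on his arm, and no section gives a reason for the early step.

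**Step 2: which feature creates which risk**

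The expectation risk depends on the patient knowing his arm when discharge is decided. A patient told on the morning of surgery knows as much as one told 45 days before, so the interval does not create this risk; disclosure does. The interval and the recheck bear on losses before surgery. Most recheck criteria are matters of fact, but some, such as intrinsic thrombotic risk, call for judgement.

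**Step 3: illustration of size**

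The protocol gives no figure from which a bias can be derived. The following shows only what an assumed shift would do.

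Inputs:
- base same-day discharge rate 60% (Objectives, Background);
- 110 patients (Study Summary), taken as 55 per arm, which assumes 1:1 allocation;
- a two-sided 5% test, assumed;
- no drug effect;
- an expectation shift *d* of 2, 5 or 10 percentage points, assumed to raise the TXA arm only.

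Method: the number discharged is Binomial(55, 0.60) without TXA and Binomial(55, 0.60 + *d*) with TXA. For every pair of counts,

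z = (p_T − p_C) / √[2·p̄(1 − p̄)/55], where p̄ = (p_T + p_C)/2.

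The probabilities of all pairs with |z| > 1.96 are summed. The same enumeration is done with Fisher's exact test.

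| Shift *d* | Patients of 55 | z-test, two-sided | z-test, favouring TXA | Fisher, two-sided |
|---|---|---|---|---|
| 0 | 0 | 5.0% | 2.5% | 3.0% |
| 2 points | 55 × 0.02 = 1.1 | 5.6% | 4.1% | 3.4% |
| 5 points | 55 × 0.05 = 2.75 | 8.7% | 8.0% | 5.7% |
| 10 points | 55 × 0.10 = 5.5 | 20.3% | 20.1% | 14.8% |

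A normal approximation gives 7.8% and 19.3% in favour of TXA for 5 and 10 points, close to the enumerated 8.0% and 20.1%.

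**Step 4: scale against the anticipated effect**

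Objectives anticipates a gain of as much as 25%. Read as percentage points (60% to 85%), a 5-point shift is 5/25 = 20% of it. Read as relative, 0.60 × 1.25 = 0.75, a gain of 15 points, and 5/15 = 33%.

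**The case against.** The strongest reply is that an open-label comparison is legitimate, that allocation at consent is an ordinary logistic choice, and that the protocol contradicts itself nowhere on this point. Its particular arguments, and what stands of each:

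- **The 45 days do not drive the main risk.** Correct. The interval is also a maximum, since screening may fall on Day 0. The disclosure point does not depend on it.
- **The argument about losses is thin.** Partly right. The criteria are first assessed before allocation, most are factual, and handling of losses in the analysis may be set out in an analysis plan that is not shown. But an analysis plan cannot make losses independent of an arm that was already known when they occurred.
- **What patients are told about benefit is not in view.** Correct. That link is conditional on the stated benefit being conveyed to them.
- **Hematuria is the main limit, and the surgeon decides.** Correct. Objectives and the end of Background name hematuria alone, and preference is one of three things the surgeon weighs. The protocol nevertheless names anxiety and preference as inputs, and that suffices for a route to the endpoint.
- **The shifts are assumed.** Correct. A 2-point shift barely changes the error rate; only the larger shifts matter.
- **The remedy is partial and its cost uncertain.** Partly right. The coordinator is described at the office consultation or by telephone, so a Day 0 step needs someone to carry it out. Bias through a surgeon who may know the arm is untouched.

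None of these supplies a reason to tell the patient his arm before the outcome is decided.

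**Conclusion.** The concern holds and should be fixed. The protocol fixes allocation and disclosure earlier than an intraoperative drug requires, and before its own eligibility recheck when the visits fall on different days. By its own account the primary endpoint is open to patient anxiety and preference.

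The sequence of events and the route to the endpoint are certain from the text. The size of the bias is not: it cannot be derived, and the illustration rests on an assumed shift, equal arms, a two-sided 5% test and no drug effect. On those terms a shift of about one patient in 55 is negligible, while one of five to six in 55 roughly quadruples the false-positive rate of the z-test (20.3% against 5.0%). Disclosure is the main fault; allocation before the recheck is secondary.

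**What to change.** 1. Move randomisation from Visit 1, item iii, to Visit 2 on Day 0, after eligibility has been reconfirmed under item iv. Amend the sentence in Recruitment Methods that ties randomisation to consent so that it agrees.
2. Delete the part of item iii under which patients are told whether they will receive TXA. State that the arm is not disclosed to the patient until the discharge and catheter-removal decision has been recorded, with unblinding available for safety.

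The first change reduces losses that depend on the arm; the second addresses patient expectation. Moving randomisation while still telling the patient would leave the expectation risk in place.

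The cost is a protocol amendment, a change in REDCap timing and an allocation step on the day of surgery. No placebo, extra visit or additional patients are needed. The changes reduce bias but do not remove it, because a surgeon who knows the arm could still be influenced.

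### The TXA safety endpoint is worded by attribution to the drug and has a scheduled item only at Day 0, which risks unequal counting against a no-TXA arm

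*Protocol*

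**What the plan says.** **Planned comparison (Protocol, Objectives).** The protocol will compare the two arms on "differences in perioperative complications associated with TXA". It gives DVT, PE and cerebrovascular events as examples and leaves the list open.

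**Endpoint (Protocol, Study Endpoints, secondary 5).** "Adverse events related to TXA (thrombotic events (DVT, PE, stroke), seizures". The list breaks off there in the text at hand.

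**Scheduled item (Protocol, Procedures Involved, Visit 2, Day 0, item v).** "Adverse Events secondary to TXA". No other line in the schedule refers to TXA events.

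**Comparator and knowledge of allocation.** Recruitment Methods gives "Group 2 (experimental): No TXA" and describes no placebo. (The arms are called TXA and no-TXA here, because the protocol attaches the label of control to the group that receives TXA.) The screening visit includes "Randomization and instructions to patients on whether or not to receive TXA".

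**Later contacts (Protocol, Procedures Involved).**
- Weekly texts ask about hematuria, dysuria, and any unscheduled visit or intervention.
- At Day 30, patients whose hematuria has already resolved get a further contact: "they will receive an additional questionnaire 30 days postoperatively to assess for bleeding complications and symptoms".
- At 12 weeks: "Will also confirm if there were or were not bleeding or other complications in first 90 days postoperatively".

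**The concern.** A comparison of harms needs the same event, counted by the same rule, in both arms. Endpoint 5 and item v instead put a judgement about the drug into the definition of the event. A coordinator who follows item v to the letter can record a pulmonary embolism in a TXA patient. The same event in a no-TXA patient has no place on that line, because it cannot be secondary to a drug that was not given. With no placebo described and patients told their arm, any attribution would probably be made with the arm known.

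Timing adds to this. The attribution-worded item sits at the day of surgery, while follow-up runs to about three months. No later contact, as described, names DVT, PE, stroke or seizure.

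What is at stake is the credibility of the safety description. The Background states that no study has yet examined TXA during HoLEP, and the Study Summary shows no data monitoring committee. Readers will therefore look at this small table for reassurance. Control-arm events that were never recorded cannot be recovered at the analysis stage, whatever an SAP says.

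**Working it through.** The protocol gives no safety event rate and no safety sample size, so it has no figure to reproduce. The check compares the passages and then illustrates the possible size.

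**1. The definitions side by side**

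| Place in the protocol | How the event is defined | Tied to TXA as cause? |
|---|---|---|
| Objectives, bleeding outcome; Study Endpoints, secondary 2 | By event (bleeding-related visits, clot retention, transfusion and so on) | No |
| Objectives, TXA complications | By type, introduced as associated with TXA, compared between arms | Ambiguous |
| Study Endpoints, secondary 5 | By type, introduced as related to TXA | Ambiguous, leaning to yes |
| Visit 2, item v | No types given; only "Adverse Events secondary to TXA" | Yes |

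The bleeding outcome works equally in both arms. The TXA safety outcome does so only if its causal wording is ignored.

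**2. What each contact can catch**

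| Contact | Asked of | Thrombotic events or seizures named? | Route by which they could be caught |
|---|---|---|---|
| Day 0, item v | Literally, TXA patients only | No; the types stand in endpoint 5 | Attribution to TXA |
| Weekly texts | Both arms | No | Unplanned visit or intervention |
| Day 30 | Those with resolved hematuria | No | Bleeding complications and symptoms only |
| 12 weeks | Both arms | No | General question on other complications |

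Two details weaken the later contacts. The heading of the weekly texts limits them to the period up to resolution of hematuria, while the paragraph beneath it runs them to the 12-week survey. If they stop at resolution, the question on unplanned visits stops too, and hematuria duration is itself an outcome that TXA may change. Also, the 12-week question covers 90 days, but 12 × 7 = 84 days, and Recruitment Methods says that no data are collected after that visit.

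**3. Illustration of size**

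Inputs: total sample size 110 (Study Summary); 1:1 allocation assumed, so 110 / 2 = 55 per arm; a true event rate r that is equal in both arms, assumed at 1%, 2% and 5%, because the protocol gives none.

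Let a be the share of TXA-arm events attributed to TXA, and c the share of no-TXA-arm events that are counted. The expected counts are 55·r·a and 55·r·c, and the spurious difference in rates is r(a − c). The extreme case is a = 1, c = 0. Counting by event type regardless of cause is a = c = 1, with no spurious difference.

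| r | Counted regardless of cause | Extreme one-sided attribution | P(at least 1 v 0) = 1 − (1 − r)^55 | P(6 or more of 55) |
|---|---|---|---|---|
| 1% | 0.55 v 0.55 | 0.55 v 0 | 42% | about 0.002% |
| 2% | 1.1 v 1.1 | 1.1 v 0 | 67% | 0.08% |
| 5% | 2.75 v 2.75 | 2.75 v 0 | 94% | 5.6% |

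**4. Could this give a false significant result?**

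For k v 0 events with 55 per arm, the two-sided Fisher p-value is 2 × C(55, k) / C(110, k). For k = 5 this is 0.057, and for k = 6 it is 0.027. At least 6 v 0 is therefore needed for p < 0.05, and the last column gives the chance of that. Even in the extreme case it is below 0.1% at a 2% rate.

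**The case against.** A reader might infer that the no-TXA arm is zero by definition and that the comparison is therefore biased. The documents do not support that. The Objectives and endpoint 5 both list event types, and a planned difference between the groups makes sense only if those types are counted in both. A fair reading is that the protocol means events of the kinds linked to TXA, in whichever arm they occur. No causality assessment, assessor or rule for discarding unattributed events is described. This stands, and it reduces the point from a certain bias to a risk created by ambiguous wording.

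A reader might also infer that safety is collected on Day 0 only. That holds for the one line that refers to TXA, not for ascertainment as a whole. The weekly texts and the 12-week question apply to both arms without reference to TXA, and a symptomatic clot, stroke or seizure would often lead to an unplanned visit. Part of this stands: later capture exists, but it is indirect.

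Nor does the protocol state that surgeons know the TXA allocation. Its one sentence on surgeon blinding concerns anticoagulation status. An open design is inferred from the absence of a described placebo and from patients being told their arm.

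The full questionnaires, case report forms and SAP are not at hand and may name these events. The break in the endpoint 5 list may come from text extraction and is not counted as an error. Neither removes the point, because the causal wording stands in the protocol text and conflicts with its own planned comparison.

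Finally, the rates are assumptions. The exclusion of patients with prior thrombosis, thrombophilia or hormonal treatment may put the true rate at the lower end. That is why a range is shown.

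**Conclusion.** The point holds as a risk of unequal counting, not as a demonstrated bias. Endpoint 5 and item v define safety events by attribution to TXA, the planned comparison is with an untreated arm, and no contact after Day 0 is described as naming the events of interest.

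The upper bound of the distortion, with equal true rates and wholly one-sided attribution, is a spurious difference equal to the event rate itself: 1, 2 or 5 percentage points at the three assumed rates, or 0.55, 1.1 or 2.75 events against none. Any control-arm counting makes it smaller. A misleading significance test is unlikely over this range. A misleading descriptive table, with one or more events against none, is the realistic harm. The figures rest on 1:1 allocation and on assumed rates. The conflict in wording rests on neither.

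This is a secondary endpoint and the primary comparison is not affected. It is worth correcting because the correction is cheap and lost control-arm events cannot be restored later.

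**What to change.** 1. In endpoint 5 and Visit 2 item v, drop the causal wording. Count DVT, PE, stroke and seizure in both arms, regardless of judged cause, and align the sentence in the Objectives.
2. State one window, from Day 0 to a single end of follow-up. Reconcile the 90-day period with a last contact at 12 weeks (84 days).
3. Record judged causality, if wanted, as a separate descriptive field that plays no part in the endpoint.
4. Add one identical yes/no item on these four events to the existing weekly text, Day 30 and 12-week contacts, for all patients in both arms. Asking it must not depend on whether hematuria has resolved.

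Cost: a few wording changes and one REDCap item in contacts already planned. Because the Day 30 questionnaire is now described only for patients with resolved hematuria, the new item would have to reach the others at that time too, which the existing text system can do. The downside is one more question for patients and slightly more data cleaning. No extra visits are needed.
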